## 1.0 Objectives

The overarching goal of this proposal is to understand the comparative effectiveness of obesity counseling as covered by Centers for Medicare and Medicaid Services (CMS) in improving weight loss for adults either with or at high risk of type 2 diabetes. CMS and most insurers now include obesity screening and counseling benefits, with no cost sharing to patients. Since overweight patients are at highest risk for diabetes, improved weight management services could prevent diabetes and its negative health outcomes. Beneficiaries with obesity are eligible for up to 20 face-to-face visits for weight counseling in the primary care setting. We propose comparing weight and diabetes outcomes in three states using electronic health record (HER) and claims data before and after this policy was implemented. The PaTH network brings together six academic health systems – the University of Pittsburgh/University of Pittsburgh Medical Center, Penn State College of Medicine/Hershey Medical Center, Temple University School of Medicine/Temple Health, and the Johns Hopkins University/Johns Hopkins Health System/Johns Hopkins Health Care, Geisinger Health Systems, and The University of Utah – to function as an integrated research network and learning health system, providing an infrastructure for observational studies, such as the one proposed here, that require populations beyond a single health system to answer important patient-centered health services questions ([www.pathnetwork.org](http://www.pathnetwork.org)). Using the PaTH Clinical Data Research Network (CDRN) infrastructure, we propose the following specific aims:

**Aim 1: Evaluate the impact of universal preventive service coverage for obesity screening and counseling on weight loss, diabetes incidence, and diabetes outcomes, in patients with diabetes or at high risk for diabetes (defined by body mass index (BMI)  $\geq 25$ ).** We will determine how the annual probability of receiving obesity and/or nutritional counseling (as defined by Current Procedural Terminology (CPT) code) changed pre- and post-policy across all insurers in a cohort of patients with diabetes and at high risk for diabetes. We hypothesize that individual patients are more likely to receive counseling following coverage implementation. Further, we hypothesize that patients who receive a greater number of face-to-face visits will have greater weight loss compared to those who receive fewer visits.

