## 2.0 Background

### 2.1 Scientific Background and Gaps

Overweight and obesity are America's number one health concern. The prevalence of obesity in the US is greater than 36%, which is far above the Healthy People 2020 objective of less than 30.5%. Perhaps most concerning is the rate that obesity has increased, having doubled since 1970. As the second most preventable cause of death, obesity is a risk factor for diabetes, cardiovascular disease, stroke, and cancer, all major causes of death in the US. Addressing obesity through lifestyle interventions decreases the risk of developing type 2 diabetes, a disease which affects over 29 million people (9.3% of the US population). Diabetes is associated with serious complications, including cardiovascular disease, blindness, renal failure and lower extremity amputation. Although complications are preventable with proper medical and lifestyle management, including weight loss, nearly half of patients with diabetes do not have adequate glycemic control.

Primary care clinics may be an ideal setting for weight control interventions. Greater than 80% of Americans see a PCP regularly and access to primary care is expected to increase with health care reform. Further, as PCPs identify and treat the multitude of conditions affected by being overweight, including diabetes, they are ideally positioned to best engage their patients in weight management. The Centers for Medicare and Medicaid Services (CMS) implemented a healthcare procedure coding system code for intensive behavioral therapy (IBT) for obesity within primary care settings in 2012 to facilitate payment for addressing obesity, which was followed by universal coverage by insurers for IBT for adults of all ages in 2013. However, the impact of this coverage on patient-centered outcomes is largely unknown.

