***Diabetes Cohort Definition.*** During year 1 of the proposed project, the investigative team, in collaboration with the PaTH Network, will identify a valid cohort of patients with type 2 diabetes. The cohort of patients under study will be defined as all patients age 18 and older with an indication of type 2 diabetes during the proposed study time frame. Patients will be classified as having diabetes using a clinically validated algorithm: type 2 diabetes mellitus on the problem list, diabetes-specific medications, hemoglobin A1c (HbA1c) results > 7.0%, or one inpatient diagnosis code or two outpatient diagnosis codes for type 2 diabetes (ICD-9 codes 250.xx). The diabetes cohort will be further limited to patients who will likely be captured in the PaTH EHR records or claims data so that outcome assessments can occur. Thus, we will further limit the diabetes cohort to patients who have either: (1) had at least 2 outpatient primary care visits in one of the PaTH health systems in the past 3 years (since January 1, 2012), or (2) for whom claims data are available. The cohort will be dynamic, with new patients added into the cohort after 2015 as they meet the diabetes cohort definition prospectively. The observational period for the outcome variables will be for the 10-year period from 2009-2019, thus including 3 years of data prior to the first policy change (CMS instituting coverage for intensive behavioral therapy for obesity) and 3 years after the last policy change (Pennsylvania Medicaid expansion) under study.

Following the definition of the diabetes cohort and key diabetes outcomes and covariates as described above, an initial extraction of variables will be conducted in Year 2 of the proposed project for years 2009-2015. This early data extraction from the PaTH Network will allow for cohort validation and data cleaning and editing, as well as required programming and determination of the analysis models. We will utilize this initial data extraction in Years 2 and 3 to analyze the impact of early health policy changes, as well as to prepare a manuscript of both the protocol and early findings of policy impact. The final data extraction will occur during the final quarter of Year 4 of the proposed project, allowing for completion of a ten-year time period (2019).

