**Table 1. Proposed Outcomes for the Pre-diabetes and Diabetes Cohorts**

Outcomes	Definition	Notes
Pre-diabetes cohort		
Weight loss during counseling	Weight lost from first IBT visit to final IBT visit	Available at all PaTH sites
Weight loss maintenance	% of weight lost during program and maintained over remaining time period, reported by year	Available at all PaTH sites
Diabetes incidence	% of patients who develop diabetes per year following weight counseling	Available at all PaTH sites
Patient-reported outcomes	-SF-12 -PHQ-2, PHQ-8, PHQ-9 -Physical function -sleep -fruit and vegetable consumption -social support -physical activity -PROMIS (PROMIS 29, physical function, depression) -healthy lifestyles -patient reported medication reconciliation	Available at some sites – Formal inventory of PROs will be collected at each institution at the beginning of the project, to be included as secondary outcomes
Diabetes cohort		
Weight loss during counseling	Weight lost from first IBT visit to final IBT visit	Available at all PaTH sites
Weight loss maintenance	% of weight lost during program and maintained over remaining time period, reported by year	Available at all PaTH sites
Patient reported outcomes	-SF-12 -PHQ-2, PHQ-8, PHQ-9 -Physical function -sleep -fruit and vegetable consumption -social support -physical activity -PROMIS (PROMIS 29, physical function, depression) -healthy lifestyles -patient reported medication reconciliation	Available at some sites – Formal inventory of PROs will be collected at each institution at the beginning of the project, to be included as secondary outcomes
Uncontrolled diabetes	Average A1c > 9 or no A1c	Available at all PaTH sites
Controlled blood pressure	SBP < 140, DBP < 90, averaged across values over year	Available at all PaTH sites
On a statin medication	Evidence of a statin medication on current EHR medication list	Available at all PaTH sites
Receiving annual eye exam	Documentation of eye exam once in past year	Available at all PaTH sites
Receiving annual urinary microalbumin test	Documentation of lab testing for urinary microalbumin at least once in past year	Available at all PaTH sites
Lower extremity amputations	Documentation of procedure for lower extremity amputation or billing code through health plans in past year	Available at all PaTH sites

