To evaluate the impact of policy changes on these outcomes, we will examine how these outcomes change over time, in response to the policy changes. As descriptive analyses, we will plot the mean trajectory of each yearly outcome at clinic level, health system level and state level. The statistical modeling of patterns of changes in individual level outcomes will be carried out through multi-level mixed-effects models. The mixed-effects model is a common and popular modeling technique for longitudinal data. A mixed-effects model can accommodate within- and between-subjects variability, as well as serial correlations. In addition, it has the flexibility to incorporate time-dependent covariates, incomplete data, and heteroscedasticity of the variances and correlations. The mixed-effects model will be specified in a multi-level fashion so that different levels of variability (e.g., individual characteristics, social environment, built environment) can be taken into account. The pattern of changes in the outcome will be assessed for pre- and post-periods, respectively, based on the piecewise/segmented regression models. The slope of each segment indicates the trend of change in diabetes outcome in that period. Therefore, the change in the trend/slope post-policy implementation may reveal the actual impact of the new policy controlling for baseline level and trend. Such modeling strategies share the same spirit of interrupted time series analysis. While the classical interrupted time series design often generates a single long series of data, we have a large number of short series from each individual subject, namely, longitudinal data. Depending on the types of the outcomes, we will specify mixed-effects models based on logistic

regression for a binary outcome, Poisson regression for a count outcome and linear regression for a continuous outcome as detailed below.

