where  $\mathbf{x}_{mijk}$  is the vector of regressors for the fixed effects,  $\boldsymbol{\beta}_m$  is the corresponding vector of fixed-effects parameter coefficients,  $\mathbf{z}_{ij}$  is a vector of cluster-level regressors for the random effects for the  $j^{\text{th}}$  cluster of the  $i^{\text{th}}$  state,  $\boldsymbol{\gamma}_{1ij}$  is the cluster-level random-effect coefficients and is common to all  $m$ , and  $\boldsymbol{\gamma}_{2mijk}$  is the subject-level random-effect coefficients associated with the parameter  $\beta_m$  for the  $k^{\text{th}}$  subject within the  $j^{\text{th}}$  cluster. The random effects are assumed to follow a multivariate normal distribution with mean zero. Because the vector  $\mathbf{x}_{mijk}$  may include subject-level, cluster-level and state-level exposure variables, the fixed effects parameter vectors  $\boldsymbol{\beta}_1$  and  $\boldsymbol{\beta}_2$  represent the effects of different exposure variables on the annual changes in the pre- and post-periods. Thus, we may perform statistical tests to examine whether there are differences in trends between the pre- and post-periods overall and for each state, and whether the patterns of changes differ between the states.

Similarly for a count outcome  $Y_{ijkt}$  (e.g., number of clinical visits), we define the expected value  $\mu_{ijkt} = E(Y_{ijkt})$  and apply a Poisson regression model based on the natural log link function. The log expected number of clinical visits,  $\log(\mu_{ijkt})$ , can be modeled with the aforementioned segmented mixed-effects model. The use of an offset term in the models yields the estimates of the rate of clinical visits rather than the mean number of visits. The fixed-effect parameters,  $\beta_1$  and  $\beta_2$ , represent the effects of exposure variables on the annual changes in log of incidence rates for the pre- and post-periods, respectively. For a continuous outcome  $Y_{ijkt}$ , we will model the mean,  $\mu_{ijkt} = E(Y_{ijkt})$ , with the mixed-effects model and the parameters  $\beta_1$  and  $\beta_2$  indicate the effects of exposure variables on the annual changes in the outcomes for the pre- and post-periods, respectively. All final statistical models will be assessed with respect to the goodness-of-fit and the appropriateness of model assumptions. Statistical software SAS 9.4 and R environment will be used to implement the proposed analyses.

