Furthermore, we will use the similar models as described above to evaluate post-policy impact of obesity screening and counseling (number of visits) on the outcomes such as weight loss, diabetes incidence, and diabetes outcomes (including hemoglobin A1c, controlled blood pressure, use of a statin medication). The outcome data collected after the universal coverage change (i.e.,  $t = 0, 1, \dots, 6$ ) will be used to estimate the trend of change. The number of screening and counseling will be used as a predictor in the mixed effects models. The effects of patient and practice characteristics will also be examined in the models. Statistical software SAS 9.4 and R environment will be used to implement the proposed analyses.

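### The plan does not fix when counseling visits are counted relative to the outcome, so with no true effect the visit coefficient can look protective, null or harmful

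*Combined protocol and SAP*

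**What the plan says.** Aim 1 (Section 1.0) hypothesizes that "patients who receive a greater number of face-to-face visits will have greater weight loss compared to those who receive fewer visits". Aim 2 compares weight and diabetes outcomes between patients who do and do not receive counseling after the coverage change.

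Section 8.0 serves both with one model. It is fitted to "The outcome data collected after the universal coverage change", at t = 0 to 6. The outcomes are weight loss, diabetes incidence, HbA1c, blood pressure control and statin use. On exposure it says: "The number of screening and counseling will be used as a predictor in the mixed effects models". The form is said to be similar to the segmented mixed model set out just before. There the regressor vector "may include subject-level, cluster-level and state-level exposure variables" and is indexed by parameter, state, cluster and subject, but not by year.

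Table 1 in Section 7.2 defines two of the outcomes by reference to counseling. Diabetes incidence is the percentage "of patients who develop diabetes per year following weight counseling". Weight loss during counseling is the change between a patient's first and last behavioral therapy session.

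**The concern.** Three things are missing: a rule that puts exposure before outcome, a start of follow-up for patients with no visits, and a weight interval that does not depend on attendance.

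- **Diabetes incidence.** If only visits before diagnosis count, a patient must stay free of diabetes to accumulate them. This is immortal time.
- **Weight, HbA1c, blood pressure, statin use.** These are repeated measures with no terminal event, so this immortal-time argument does not apply. The risk is reverse causation: current status influences whether the patient attends.
- **Weight between first and last session.** The outcome is undefined for 0 visits, zero by construction for 1 visit, and spans a longer time as visits increase.

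This model carries the visit-number hypothesis and Aim 2. Section 8.0 expects power for very small effects and relies on the investigators to judge whether significant results matter clinically. That safeguard does not help here, because a spurious halving of diabetes incidence would look clinically important.

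**Working it through.** **1. Outcome window.** Universal coverage is dated by "followed by universal coverage by insurers for IBT for adults of all ages in 2013". The end of data comes from "The observational period for the outcome variables will be for the 10-year period from 2009-2019". 2019 - 2013 = 6, so t = 0 to 6 gives 7 yearly points, which agrees with Section 8.0. The plan states no effect size, event rate or alpha for this analysis, so there is no other figure to reproduce.

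**2. How the count enters as written.** Take the post-policy part as an intercept plus a slope in t, and put a subject-level count N into both. The linear predictor at year t then contains b0·N + b2·t·N. N is the same at every t. A visit in 2018 (t = 5) therefore contributes to the fitted value for 2014 (t = 1).

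**3. Diabetes incidence, true effect zero.** At an assumed 1.0 visit per year, a patient free of diabetes throughout expects 1.0 × 7 = 7 visits. A patient diagnosed at the end of the second year expects 1.0 × 2 = 2 if counting stops at diagnosis. The count then partly measures time without diabetes.

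The simulation used 40,000 people per scenario, 7 years, and a discrete-time logistic model with year terms and no random effects. Assumed inputs were:
- annual incidence 2% or 5%;
- mean 0.3 or 1.0 visits per year, varying between people and independent of risk;
- visit rate after diagnosis multiplied by 0, 1 or 3.

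That makes 2 × 2 × 3 = 12 scenarios.

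| How visits are counted | OR per visit | OR any vs none |
|---|---|---|
| Whole-window total, stopped at diagnosis | 0.75-0.76 (0.3/yr); 0.88-0.89 (1.0/yr) | 0.33-0.42 |
| Whole-window total, rate unchanged after diagnosis | 0.99-1.00 | 0.98-1.10 |
| Whole-window total, rate tripled after diagnosis | 1.05-1.17 | 1.76-1.92 |
| Cumulative to end of previous year (all 12 scenarios) | 0.99-1.01 | not run |

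The 1.10 in the second row has a 95% interval of 1.01 to 1.20. The other three values in that cell are 0.98, 1.00 and 1.02. A separate null simulation (400,000 patients, incidence 3% or 8%, counseling uptake 3% or 10% per year) gave ever versus never ratios of 0.46-0.56 with counting stopped at diagnosis and 1.00-1.01 with all counseling counted.

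**4. Weight from first to last session, true effect zero.** Patients had 2 to 20 visits, with an assumed SD of 1 kg between visits.
- Losing weight promotes attendance: a spurious 0.20-0.27 kg lost per extra visit.
- Lack of loss promotes attendance: -0.19 kg lost per visit, an apparent harm.
- Attendance independent of weight: 0.00.

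**5. Yearly HbA1c, true effect zero, random-intercept model.**
- High HbA1c prompts visits: +0.18 points per visit.
- Low HbA1c goes with attendance: -0.19.
- Neither: 0.01 (SE 0.005).

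**6. Which baseline to adjust for.** Suppose each visit has a true, lasting effect of -0.3 kg in the year it occurs. Let V be visits in a year and C cumulative visits: W(t) = W(t-1) - 0.3·V(t) + error.
- Given W(t-1), the effect of C(t-1) is already contained in W(t-1), so its coefficient tends to 0. Simulation returned 0.00 to -0.05.
- Given the pre-exposure weight W(0), W(t) = W(0) - 0.3·[C(t-1) + V(t)] + errors, so the coefficient on C(t-1) is about -0.3. Simulation returned -0.30 to -0.35. An excess over 0.30 is expected when patients differ in visit rate, because V(t) then correlates with C(t-1).

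Lagged and landmark counts also restored the incidence null in a further check (0.97-1.01).

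**The case against.** The strongest reply is that Section 8.0 is silent, not wrong. The first-level unit is the yearly measurement, and receipt of counseling is among the outcomes summarized yearly. Of the mixed model the plan says "it has the flexibility to incorporate time-dependent covariates". Section 7.2 leaves determination of the analysis models to the early data extraction. A lagged count fits all of this.

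That reply stands as far as it goes. A reader might infer that the plan builds in the bias, but the text does not prescribe a whole-window total. The flexibility is mentioned as a general property of mixed models, however, and is not applied to the visit count. The written regressor vector points to one value per subject.

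A reader might also infer that immortal time is certain and that the bias always favors counseling. The documents do not support either. No section stops counting visits at diagnosis. Counseling is studied in the diabetes cohort too, and no rule removes a patient from the at-risk cohort at diagnosis. With all visits counted at an unchanged rate, the incidence bias disappears. Where diagnosis or worse status prompts visits, its sign reverses.

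Table 1 cuts both ways. It places diabetes onset after counseling, which orders events for counseled patients. It leaves the uncounseled without a start date and makes time before a first visit event-free by definition.

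The propensity score analysis does not close the gap. It is only under consideration, is directed at the policy effect, and has no rule on exposure timing.

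**Conclusion.** The concern holds in this form: the plan permits a visit count that overlaps or follows the outcome it predicts, and it contains no rule that prevents this. With no true effect, the coding choice and the attendance pattern decide the answer. The any-versus-none ratio for diabetes is about 0.3 to 0.55 if visits count only until diagnosis, near 1 if all visits count at an unchanged rate, and 1.76 to 1.92 if visits triple after diagnosis. Spurious weight effects are roughly 0.2 kg per visit in either direction, and spurious HbA1c effects nearly 0.2 points per visit in either direction.

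These sizes rest on assumed incidence, visit rates and attendance behavior, none of which the documents give. They show what can happen; they do not predict the study's bias. The claim that visits will necessarily look protective is not supported. The immortal-time argument is confined to diabetes incidence.

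Because this model tests the visit-number hypothesis and Aim 2, the timing should be fixed before the analysis is run.

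**What to change.** Add the following to Section 8.0:

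1. **Index date** for every patient, including those with no visits, by a rule that does not depend on counseling (for instance, first meeting the cohort definition on or after the coverage change). Diabetes incidence is counted from this date in both groups.
2. **Exposure**: cumulative visits to the end of year t-1, updated yearly, as the predictor of the outcome in year t.
3. **Adjustment** for the pre-exposure baseline value (weight, HbA1c), not the prior-year value, which absorbs the effect of earlier visits.
4. **Weight change** over fixed calendar intervals from index for this comparison. The first-to-last-session measure can stay as a description of counseled patients.
5. **Landmark analysis**: visits in the first 12 months after index, outcomes only after month 12, adjusted for index weight or HbA1c.
6. **Reporting** as an association.

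The cost is SAP wording and programming, plus some information. The first year gives exposure but no outcome, so a patient indexed at t = 0 contributes at most 7 - 1 = 6 outcome years. Patients diagnosed before month 12 leave the landmark incidence analysis. The estimand also changes, to the association with past visits and not those of the same year.

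The lag removes the timing bias for incidence. It does not remove confounding by indication or engagement. With baseline adjustment only, weight or HbA1c during follow-up can still influence later attendance. If a causal reading is wanted, a method for time-varying confounding would be needed as well.
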